2.2. Secondary Objectives

1. To determine whether the decision impact of the GC test is of benefit to patients. Specifically, is net benefit of GC use superior to those who do not have the GC test as assessed by decision curve analysis.
2. To determine whether use of the GC test results in decreased likelihood of adjuvant treatment for subjects with high CAPRA-S score (≥ 5) and increased adjuvant treatment for subjects with low CAPRA-S score (< 5). The hypothesis is that there is a non-zero interaction between GC test use and CAPRA-S.
3. To determine whether GC use is associated with earlier use of salvage therapies in CAPRA-S low risk patients and later use of salvage therapy in CAPRA-S high-risk patients.

4. To determine whether use of GC results in improved protection from BCR and metastatic progression.
5. To investigate the impact of GC use on QOL, and whether there is differential QOL impact among CAPRA-S high- and low-risk patients.
6. To determine whether collaborative-wide education and the use of CAPRA-S scores in the control group impacts rates of adjuvant radiotherapy compared to historical controls.

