6.1. FFPE Block Selection/Specimen Acquisition

FFPE (formalin fixed paraffin embedded) tissues from RP prostate tumor sample blocks will be collected from patients in both the GC and UC arms for transcriptome-wide expression analysis.

The FFPE block from the RP that exhibits a) highest Gleason Score, AND b) highest percent tumor involvement will be selected for sampling with at least 60% tumor by surface area. The pathologist will mark the H&E slide that will be used to guide punching. The marked area should preferentially sample tumor with the highest Gleason grade (e.g., in a 4+3 lesion, the pattern 4 component should be enriched in the punch specimen). Two (2) X 1.5 mm in diameter punches will be sampled from the RP FFPE block (e.g., using a tissue microarray core device or a disposable punch tool, to be provided by GenomeDx). Each punch will be placed in a separate microfuge tube and stored at 4°C until shipping.

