7.3. Statistical Methods Supporting the Secondary Objectives

All tests will be two sided at a 0.05 significance level. Individuals who are lost to follow-up will be considered censored in time to event analyses. Treatment plans available at the time of drop-out will be considered the final treatment plans.

Secondary Objective 1: To determine whether the net benefit to subjects in the GC arm is superior to the UC arm. This will be determined by directly calculating the net benefit (Vickers and Elkin 2006) across a range of treatment thresholds, Decision Curve Analysis (DCA). DCA is a method for assessing prognostic models that incorporates clinical consequences and the potential probability thresholds at which the likelihood of a given outcome (eg: progression to metastatic disease) may influence the treatment decision of a patient and their physician. For example, one individual may choose treatment if there is a 5% chance of a given outcome while another individual may not be influenced unless the likelihood of that outcome is as high as 10 or 15%. Thus, this methodology allows for how different patients may differentially weigh false negative or false positive results. The calculated net benefit is plotted against threshold

probabilities, and different prediction tools (eg. CAPRA-S and GC) can be compared across these probabilities. If GC is not superior to UC across all thresholds, the region of superiority will be evaluated to determine if it contains a clinically meaningful ratio of harm due to unnecessary treatment versus missed treatment.

Secondary Objective 2: To determine whether use of the GC test result results in decreased likelihood of treatment for CAPRA-S high and increased likelihood of treatment for CAPRA-S low, a modeling approach similar to that of supporting the Primary Objective will be used, but with a GC-by-CAPRA-S interaction term as follows:

$$\text{logit}\left(\frac{\pi_{ijk}}{1-\pi_{ijk}}\right) = \beta_0 + \beta_1 G_i + \beta_2 (G_i * GC_i) + \beta_3 CAPRA-S_i + \beta_4 (G_i * CAPRA_i * GC_i) + \gamma_j + \phi_k$$

where parameters are defined as previously. The test of $H_0: \beta_4 = 0$ will be performed using a Type III test (SAS PROC GLIMMIX). The direction of the interaction will be evaluated graphically with the probability of treatment based on the model and for empirical probabilities using pre-defined GC and CAPRA-S cutoffs.

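### Secondary Objective 1 judges net-benefit superiority from point estimates over an unstated threshold range, with no interval or test, and separately uses a GC arm in which the score informed treatment

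*Combined protocol and SAP*

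**What the plan says.** Section 2.2 poses the objective as a question of superiority: "is net benefit of GC use superior to those who do not have the GC test as assessed by decision curve analysis". Section 7.3 answers it by calculating net benefit directly over a range of thresholds and plotting it, and adds that "different prediction tools (eg. CAPRA-S and GC) can be compared across these probabilities".

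The range is not stated. The only thresholds mentioned are illustrations: "one individual may choose treatment if there is a 5% chance of a given outcome", while another person may not be influenced "unless the likelihood of that outcome is as high as 10 or 15" per cent. The outcome is also given only as an example, progression to metastatic disease.

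The first criterion is superiority at every threshold. Failing that, a fallback applies: "If GC is not superior to UC across all thresholds, the region of superiority will be evaluated", the question being whether that region includes a meaningful ratio of harm from unnecessary versus missed treatment. The plan does not say what ratio is meaningful.

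Section 7.3 opens by setting two-sided tests at 0.05, but names no net-benefit test for that line to govern. By contrast, it names a Type III test for Objective 2, frailty models for Objectives 3 and 4, and ANCOVA with confidence intervals for Objective 5.

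Under Study Design (Section 3), GC and CAPRA-S are both disclosed in GC periods to inform the treatment plan, and CAPRA-S alone in UC periods. Section 6.1 says that tissue "will be collected from patients in both the GC and UC arms for transcriptome-wide expression analysis".

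**The concern.** There are two separate problems.

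**Chance.** Two net-benefit curves from different patients differ by sampling error even when the tools are equally good. If superiority is read from point estimates, and a favourable stretch may be picked out once the curves are visible, nothing in the rule limits how often a useless test appears superior somewhere. Objective 1 is the plan's direct question on whether the decision impact benefits patients, so a false positive here would be quoted.

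**Treatment feedback.** Net benefit counts a high-risk patient who has the event as a true positive and one who does not as a false positive. In the GC arm the score influences who is treated. If treatment prevents events, some would-be true positives become apparent false positives, and the event rate in the arm changes as well. The GC curve then reflects treatment as well as prediction.

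**Working it through.** The documents give no power, precision or error rate for net benefit, so there is no plan figure to reproduce. The 83% power in Section 7.5.2 concerns the primary test of the GC score.

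**Inputs.**
- From the documents: 550 subjects (Section 3), so 550/2 = 275 per arm. The power statement uses 350 (Section 7.5.2), so 350/2 = 175 per arm.
- From the documents, as illustrations only: thresholds of 5% to 15%, taken in 1% steps (11 thresholds).
- Assumed: outcome rates of 5%, 10% and 20%; AUC 0.75 for the tool in each arm; calibrated risks; no clustering.

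**Formulas.** At threshold pt,

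NB(pt) = TP/n − (FP/n) × pt/(1 − pt).

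Scores are normal with unit variance and shifted by d in patients with the event, where d = √2 × Φ⁻¹(0.75) = 1.414 × 0.674 = 0.95. Predicted log-odds are logit(p) + d·x − d²/2. Both arms use the same tool, so the true difference is zero at every threshold.

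**Result, 275 per arm, thresholds 5-15%: GC above UC by point estimate.**

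| Outcome rate | Some threshold | Three or more consecutive | Whole range |
|---|---|---|---|
| 5% | 75% | 61% | 24% |
| 10% | 70% | 57% | 30% |
| 20% | 61% | 54% | 37% |

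Repeat runs moved these by about 2 points at most. At 175 per arm the first column is 75/68/62%. With a wider 2-20% range at 275 per arm it is 84/76/68%.

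**A different null model.** Here GC is unrelated to outcome, CAPRA-S has an assumed OR of 1.35 per point, and event rates are 3-35%. GC is above UC at some threshold in 52-84% of trials, over three or more consecutive thresholds in 48-67%, and over the whole range in 3-49%.

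**What an interval does.** In that second model, at 275 per arm:
- Point estimate alone at one threshold (10%, illustrative): GC is higher in 49-51% of trials.
- 95% interval at that one pre-set threshold: a false finding for GC in 2.4-2.9%.
- Pointwise 95% intervals with any of the 11 thresholds allowed to count: 3.9-8.7%.

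**What the harm-ratio filter does.** Each threshold fixes its own ratio: 0.05/0.95 is 1 to 19, and 0.15/0.85 is about 1 to 5.7. The ratio depends on the threshold and not on the data. Asking whether a region contains a meaningful ratio restricts where a chance region may fall, but does not test whether it is chance.

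**Treatment feedback.** In large simulated samples (200,000 per arm), treatment has an assumed OR of 0.4 on the event and the threshold is 10%. Base event rates are 6% and 25%.
- GC uninformative, treatment in the GC arm falling from about 5% to 2.5%: the between-arm difference is +0.3 per 1000 (6%) and +4.9 per 1000 (25%).
- GC uninformative, treatment rising to about 14.5%: −1.4 and −12.3 per 1000.
- With no treatment effect, the same runs scatter by up to about 0.4 (6%) and 1.1 (25%) per 1000, so the +0.3 is indistinguishable from zero.
- GC truly prognostic, 6% base rate, GC raising treatment: the gain measured within the GC arm shrinks from about 7-8 to about 4 per 1000.

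**The case against.** The strongest reply is that the plan never says one crossing establishes superiority. It first asks for superiority at all thresholds and only then examines a region, through a clinical filter that may fail. This stands: the 61-75% figure describes how often a chance region exists, not the plan's error rate. It does not rescue the rule. Even the strict criterion, read from point estimates, is met in 24-37% of null trials, against 2.5% in one direction for a two-sided 0.05 test.

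A reader might also infer that a false region is likely because the score directed treatment. The documents do not support that. The chance figures contain no treatment effect, and treatment feedback can work the other way. In a strong contrast (assumed: the top 10% of GC-arm scores treated, half their events prevented, UC untreated), GC lies above UC somewhere in 5-15% in only 48/37/29% of trials at outcome rates of 5/10/20%. A certain downward bias is not supported either, since the sign between arms follows treatment use.

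The AUC, outcome rates and treatment effect are all assumed, and 5-15% is the plan's illustration, not its planned range. Finally, Objective 1 is not the only evidence on patient benefit: Objective 4 compares BCR and metastatic progression, and Objective 5 compares QOL. The primary objective is untouched.

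**Conclusion.** The concern holds in a limited form. As written, Objective 1 judges superiority without any measure of sampling error and allows the favourable region to be found after the curves are seen. Under no true difference, some apparent region within 5-15% arises in about 61-75% of trials, a run of three or more steps in about 54-61%, and superiority over the whole range in about 24-37%. These figures rest on 275 per arm, AUC 0.75, outcome rates of 5-20% and no clustering. The second null model gives wider ranges (52-84%, 48-67% and 3-49%) and the same conclusion.

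Treatment feedback is a separate validity problem of uncertain direction. It makes a GC-arm decision curve hard to interpret, but is not itself a source of false superiority. Nor does the text support saying that the plan will declare superiority from any crossing. The defect is that it leaves the rule open. The plan should be changed; the consequence is confined to a secondary objective.

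**What to change.** In Section 7.3, before analysis:

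1. Name the outcome and time point (for example BCR or metastasis at 3 years, both already endpoints in Section 5.2), the threshold range, and the harm ratio that counts as clinically meaningful. The sponsor chooses the values.
2. For GC use as a strategy, which is what Section 2.2 asks, compare the arms as randomised. For each arm compute event rate + w × adjuvant treatment rate, with w set from the pre-specified threshold and its derivation stated, because this sum counts every treated patient and not only false positives. Give centre-level bootstrap intervals for the difference.
3. Claim superiority only at one pre-set threshold whose 95% interval excludes zero, or where a simultaneous band over the range excludes zero. Pointwise intervals over the range are not enough (3.9-8.7% above).
4. As a separate analysis of prognostic value, compare CAPRA-S with CAPRA-S plus GC in the same UC patients, whose treatment was not guided by GC. Correct for overfitting: refitting an uninformative GC within one arm without correction shows an apparent gain at one or more of the 5-15% thresholds in 65-96% of null trials. State that GC scores will be generated from the UC tissue. This analysis does not answer the question about GC use and should not be reported as if it did.

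The cost is SAP wording and a bootstrap, plus assay of UC tissue if that is not already planned. With about fourteen centres, the coverage of a centre-level bootstrap should be checked by simulation. The within-UC comparison has fewer subjects and events, and superiority becomes harder to claim.

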7.1. Statistical Methods Supporting the Primary Objective

The Primary Objective of this study is to determine the impact of GC test result on adjuvant treatment decisions compared to clinical factors alone. This will be evaluated by testing for an effect of GC score in a regression model which adjusts for CAPRA-S risk score. As a cluster-crossover trial, a generalized linear mixed effects model will be used to model the probability of a subject receiving adjuvant treatment within center, in a specific period of the study. Since GC score is a subject-level covariate, an individual-level regression model is utilized rather than a cluster-level aggregated analysis (Campbell 2014, Chapter 6). Specifically, the model to be fit is

$$\text{logit}\left(\frac{\pi_{ijk}}{1-\pi_{ijk}}\right) = \beta_0 + \beta_1 G_i + \beta_2 (G_i * GC_i) + \beta_3 \text{CAPRA-S}_i + \gamma_j + \phi_k$$

where π_{ijk} is the probability of treatment for the i^{th} subject enrolled in the j^{th} cluster (ie: center) during the k^{th} period, G_i is the group to which the subject is enrolled (GC=1, UC=0), CAPRA-S_{*i*} is that subjects' CAPRA-S score (0-12), GC_{*i*} is the GC score (0-1), $\beta_0 \sim N(\mu, \sigma^2)$ and

$\phi_k \sim N(0, \sigma^2)$ are random cluster and period effects, respectively. The null hypothesis $\beta_2 = 0$ will be tested using a Type III test (SAS PROC GLIMMIX) at a 0.05 significance level. 95% confidence intervals using robust variance estimates will also be calculated.

In addition to the model described above, an additional model including a group-by-period interaction term will be fit to ensure that group assignment in a period is not effected by preceding or subsequent periods. For the purposes of this analysis, the period effect will be

considered fixed. This may detect carry-over effects if behaviors or attitudes of physicians within sites persist or change over the course of the study or if changes in patient education materials or their presentation change from one period to the next. Should this interaction term be significant, an alternative analysis utilizing non-consecutive periods may be used.

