Descriptive statistics for various quantities, including raw treatment rates (and 95% confidence intervals) of adjuvant treatment and type of treatment (hormone and radiation) for discrete risk categories for both CAPRA-S (low-risk 0-4, high-risk ≥ 5) and GC (low-risk ≤ 0.45 , high-risk > 0.45) as well as by clinical center and period. Model-based predicted probabilities of treatment will be calculated for various combinations of CAPRA-S and GC high and low risk along with associated confidence intervals.

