Secondary Objective 3: Time-to salvage therapy initiation will be modeled using a Cox formulation of a Frailty regression model with a similar formulation (ie: main and random effects) to that used for the primary analysis. Kaplan-Meier curves for GC and UC arms will be plotted, as well as for combinations of high- and low-risk GC and CAPRA-S groups.

Secondary Objective 4: Time-to BCR and metastatic progression will be evaluated similarly to the model described for Secondary Objective 3.

Secondary Objective 5: Summary statistics for all QOL instruments and corresponding confidence intervals will be calculated and compared for the GC and UC subjects and shown graphically over time. Validated instruments are used to measure erectile function, urinary function, sexual interest, and sexual satisfaction. Scores for each domain will be scaled with a minimum to maximum range of 0-100. Comparisons between GC and UC subjects will be made at each timepoint (3, 6, 12 and 24 months after surgery) and on each domain and overall score (VAS 0-10), using an ANCOVA analysis including adjustment for time since surgery. Should the assumptions for ANCOVA not be met (strongly skewed data or substantial ceiling or floor effect) a semiparametric ANCOVA model will be used (as in Buja 1989) to adjust for time-from surgery. If the distribution of time-from surgery is similar in the two groups, a Mann-Whitney test for differences will be used to corroborate the ANCOVA model. For this secondary objective, there will be no adjustment for multiple comparisons across domains or time points.

Exploratory Objective: Using a variety of budget models the cost of care for patients in the GC vs. UC arms will be compared out to 3 years from surgery. This will include estimated costs for adjuvant therapy. Differences in total cost, and differential cost per patient (UC vs GC) will be calculated and compared using either standard t-tests if data is normally distributed or appropriate non-parametric test if data is right skewed.

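### Secondary Objective 2 tests a three-way term instead of its stated arm-by-CAPRA-S interaction, and Secondary Objective 3 has no arm-by-CAPRA-S test

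*Combined protocol and SAP*

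**What the plan says.** **Secondary Objective 2.** Section 2.2 expects GC test use to lower adjuvant treatment at CAPRA-S 5 or more and to raise it below 5. It then states: "The hypothesis is that there is a non-zero interaction between GC test use and CAPRA-S". Section 7.3 says that "a modeling approach similar to that of supporting the Primary Objective will be used, but with a GC-by-CAPRA-S interaction term as follows". The printed linear predictor is β0 + β1·G + β2·(G × GC) + β3·CAPRA-S + β4·(G × CAPRA-S × GC) plus random centre and period effects, and the test is of β4 = 0. Section 7.1 defines G as the arm (GC = 1, UC = 0) and GC as the assay score from 0 to 1, so the β4 term is three-way. On the sign of the effect, Section 7.3 adds: "The direction of the interaction will be evaluated graphically".

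**Secondary Objective 3.** Section 2.2 asks whether GC use goes with "earlier use of salvage therapies in CAPRA-S low risk patients and later use of salvage therapy in CAPRA-S high-risk patients". Section 7.3 gives a Cox frailty model "with a similar formulation (ie: main and random effects) to that used for the primary analysis". It adds that "Kaplan-Meier curves for GC and UC arms will be plotted", along with curves for combinations of GC and CAPRA-S risk groups. No test accompanies the curves.

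**The concern.** Both objectives concern effect modification: does the effect of being in the GC arm differ by CAPRA-S? The natural parameter is the arm × CAPRA-S coefficient, and neither analysis contains it.

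For Objective 2, the plan could declare the hypothesis supported or unsupported on a coefficient that describes something else. The β4 term is zero for every UC patient. It therefore measures whether the influence of the GC score among tested patients changes with CAPRA-S.

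For Objective 3, effects in opposite directions cancel in a single arm coefficient. A true pattern of the hypothesised kind could give a null result, and the two directional claims would rest on reading plotted curves.

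**Working it through.** The documents state no power for either objective, so there is no figure to reproduce. The main check is algebra on the printed model; the simulations only show size.

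**1. What β4 measures.** At CAPRA-S c and GC score g, within the same centre and period, the arm difference in log odds is

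β1 + β2·g + β4·c·g.

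Its change per CAPRA-S point is β4·g: 0.1·β4 at g = 0.1, 0.45·β4 at g = 0.45, 0.9·β4 at g = 0.9, and zero at g = 0. CAPRA-S can modify the arm effect only in proportion to the GC score. Section 2.2 states no such restriction.

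**2. Dependence on coding.** Replacing g by g − a in the three-way term gives β4·c·g − a·β4·c. The second part is an arm × CAPRA-S term, which the model cannot absorb because it has none. So the β4 test depends on where the score's zero lies. In simulation (550 patients, 9–10% treated, arm × CAPRA-S effect of −0.3 per point, 1000 trials), subtracting 0.4 from the score cut β4's rejection rate from 33% to 6%.

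**3. Objective 2 simulation.**
- From the documents: 550 patients (Section 3); 14 sites with the Section 7.5.1 enrolment weights (site 5 is not listed; 4 per month assumed); two GC and two UC periods per site; site variance 1 (ICC 23%) and period ICC 3% (variance 0.13); CAPRA-S OR 1.15, taken per point; about 8% treated among CAPRA-S high-risk patients (Section 7.5).
- Assumed: GC score Beta(2,3); CAPRA-S mean 4.2, SD 2.0, with 44% at 5 or more; correlation between the scores 0.29; score OR 1.47 per 0.1, in the GC arm only; all other effects and rates.
- Method: penalised logistic mixed model with variance components held at their generating values; 4000 trials per setting (Monte Carlo SE at most 0.8 points). The direct model has G, CAPRA-S and G × CAPRA-S.

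Each cell gives the rejection rate at three treatment rates: 8% in UC patients with CAPRA-S 5 or more (about 7% overall) / 10% overall / 20% overall.

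| True effect | β4 test | Direct G × CAPRA-S test | Direct slope per point |
|---|---|---|---|
| No arm effect | 5–6% | 5–6% | – |
| Arm × CAPRA-S, −0.2 | 13/17/26% | 18/24/38% | – |
| Arm × CAPRA-S, −0.3 | 24/32/50% | 36/46/69% | – |
| Three-way only (both scores centred) | 20/23/30% | 7/7/6% | +0.04/+0.03/+0.01 |
| GC-score effect only | 5% | 9/10/12% | +0.11/+0.10/+0.10 |
| GC-score effect plus −0.2 | 14/18/28% | 7/7/11% | −0.08/−0.08/−0.09 |

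β4 holds its 5% level when there is no interaction and picks up part of a two-way effect. Otherwise the two tests diverge in both directions.

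**4. Objective 3.** The primary model's fixed terms are G, G × GC and CAPRA-S. Whether or not G × GC is carried over, there is no G × CAPRA-S term. Assumed for illustration: 550 patients, exponential hazards, lognormal centre (variance 0.25) and period (0.02) effects, 3-year follow-up, 3-year salvage of 15% / 30%, and 2000 trials per setting (SE at most 1.1 points).

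| Arm HR at CAPRA-S <5 and ≥5 | Single arm HR | Arm test rejects | G × CAPRA-S rejects |
|---|---|---|---|
| 1.5 and 0.67 | 1.04 | 5/6% | 29/52% |
| 1.5 and 0.8 | 1.12 | 8/11% | 19/34% |
| 1.25 and 0.67 | 0.93 | 6/7% | 19/35% |
| 1.25 and 0.8 | 1.01 | 5/6% | 12/19% |

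Hand check of the first row. Averaging the log hazard ratios over a 56%/44% split gives 0.56 × 0.405 − 0.44 × 0.400 = 0.05, an HR of about 1.05. At 15% salvage there are 550 × 0.15 = 82.5 events, split 46.2 and 36.3. The SE of the interaction is √(4/46.2 + 4/36.3) = 0.444, and log(1.5/0.67)/0.444 = 1.82. With CAPRA-S split at 5, power is Φ(1.82 − 1.96), about 44%. A linear CAPRA-S term captures a step at 5 with correlation about 0.394/√(0.56 × 0.44) = 0.79. This gives z = 1.44 and power of about 30%, in line with the 29% above.

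**The case against.** The strongest reply is that the direct test is not generally more powerful. The rows where it wins assume that the GC score has no effect on treatment, contrary to the trial's primary hypothesis. Once a score effect is added, β4 rejects more often (14/18/28% against 7/7/11%). This stands, so the case for change does not rest on power. It rests on the test addressing the stated hypothesis.

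A related point is that the direct interaction is marginal over the GC score. If the score alone drives treatment and correlates with CAPRA-S, the marginal slope is about +0.1, opposite to the hypothesised direction. An alternative keeps G × GC in the model and tests G × CAPRA-S given the score. In runs of 1000 trials under score effect plus −0.2, at treatment rates of about 7% and 20%, that test rejected 19% and 35%. With the score effect alone it rejected 4–5%. This also stands: the plan must name its estimand. The wording about GC test use in Section 2.2 points to the marginal one.

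The three-way-only row depends on centring both scores. With an uncentred coefficient of −0.5, the marginal slope is −0.20 and both tests respond (24% against 19% at a 7% rate, 50% against 37% at 19%). That limits the example but leaves the algebra untouched.

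Section 7.1 does plan treatment rates and predicted probabilities with confidence intervals by risk category. These are descriptive, are not specified by arm, and the predictions come from a model without arm × CAPRA-S.

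For Objective 3, the single hazard ratio applies only if G × GC is dropped; if it is kept, the arm coefficient is the effect at GC score zero. Neither reading tests the hypothesis.

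**Conclusion.** The concern holds for both objectives. For Objective 2, the tested coefficient answers a different question from the hypothesis in Section 2.2; this follows from the printed equation without any assumption. For Objective 3, the stated hypothesis has no formal test.

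The practical size is uncertain because score distributions, effects and most event rates had to be assumed. At the documents' own treatment rate and an effect of −0.2, both Objective 2 tests have low power and differ by 5 points (13% against 18%). Elsewhere they differ by up to 24 points (20% overall, three-way only: 30% against 6%). These are secondary objectives; the primary test of β2 and the sample size are unaffected. The text should be corrected before the arm comparison is analysed, so that the choice of model is not made after seeing results.

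**What to change.** **Objective 2.** Fit G, CAPRA-S and G × CAPRA-S with centre and period effects. Test G × CAPRA-S and report arm differences at CAPRA-S below 5 and at 5 or more. State that this is the marginal effect of test use by CAPRA-S, averaged over GC score, so correlation between the two scores contributes to it. If the sponsor intends the effect conditional on GC score, the SAP and Section 2.2 should both say so. Keep the three-way model as exploratory, with G × CAPRA-S included.

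**Objective 3.** Add G × CAPRA-S to the frailty Cox model, test it, and report arm hazard ratios within the two CAPRA-S groups. State whether CAPRA-S enters the interaction as the score or split at 5.

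**Clarification for Objective 4**, which borrows the Objective 3 model: state that the tested contrast is the arm coefficient from a model with G and CAPRA-S and without G × GC.

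The cost is SAP wording only, with no new data, visits or patients.

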One such assay is Decipher from GenomeDx Biosciences, a GC assay developed and validated in a post-RP setting as a predictor of eventual metastasis (Erho 2013). Studies have demonstrated independent prognostic value of this GC assay above and beyond standard clinicopathologic parameters reclassifying the clinically high-risk men tested into lower or significantly elevated risk of metastatic disease progression (Karnes 2013, Den 2014, Cooperberg 2015, Klein 2015, Den 2015, Ross 2015, Yamoah 2015). Studies have demonstrated that Decipher low risk patients can safely delay/defer treatment and avoid the adverse side effects of radiation treatment after radical prostatectomy while Decipher high risk patients can benefit from early adjuvant radiation (Den 2014, Den 2015).

In addition to clinical validation, several decision impact studies of Decipher were conducted to investigate a GC's influence on physicians' post-radical prostatectomy treatment recommendations (Badani 2013, Badani 2014, Michalopoulos 2014, Nguyen 2015).

Badani (2013) evaluated the influence on urologist treatment recommendations with GC in comparison to clinicopathologic risk factors alone for patients from a tertiary care center. This prospective, pre-post design study showed that among twenty-one high volume (i.e., mean 180 RP/year) urologic surgeons from 18 US institutions who were asked to make treatment recommendations for 24 prostate cancer patient cases post-RP, 43% changed their treatment recommendation with the addition of genomic information to standard clinicopathologic information.

To further reflect the distribution of test results and risk of metastasis among high-risk patients seen in a broader range of clinical settings other than academic centers, a prospective, multi-center, decision-impact study (ASSESS-D, Badani 2014) evaluated the effect of knowledge of the GC model on urologist treatment decision-making in a population of patients having undergone radical prostatectomy in a community-based practice. One hundred ten patient case histories were available for review by 51 urologists. Overall, 31% (95% CI: 27- 35%) of treatment recommendations changed with knowledge of GC. Treatment intensity was strongly correlated with the GC-predicted probability of metastasis ($p < 0.001$) and the GC was the dominant risk factor driving decisions in multivariable analysis (OR=8.6, 95% CI: 5.3-14.3%, $p < 0.0001$).

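### The Cox models for Secondary Objectives 3 and 4 are defined only by reference to the primary model; if its terms are carried over, no coefficient answers Objective 4 and the arm term drifts toward false protection

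*Combined protocol and SAP*

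**What the plan says.** Objective 4 (Section 2.2) is: "To determine whether use of GC results in improved protection from BCR and metastatic progression". That is a comparison of arms. Objective 3 in the same section predicts opposite effects on salvage timing: earlier in CAPRA-S low-risk men, later in CAPRA-S high-risk men.

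For Objective 3, Section 7.3 proposes a Cox frailty model "with a similar formulation (ie: main and random effects) to that used for the primary analysis". For Objective 4: "Time-to BCR and metastatic progression will be evaluated similarly to the model described for Secondary Objective 3". No survival formula is written and no coefficient is named as the one to be tested. Kaplan-Meier curves by arm are planned for salvage, but no arm-only test accompanies them. The general rule is: "All tests will be two sided at a 0.05 significance level".

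The primary formula in Section 7.1 has three fixed terms: arm (G, 1 for GC and 0 for usual care), the product G*GC, and CAPRA-S. It adds random center and period effects. The GC score runs from 0 to 1, is not centered, and has no main effect. The tested coefficient there is that of G*GC, which "will be tested using a Type III test (SAS PROC GLIMMIX) at a 0.05 significance level".

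Section 1 reports "independent prognostic value of this GC assay above and beyond standard clinicopathologic parameters", with metastasis as the outcome. Section 6.1 says tissue is collected in both arms.

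**The concern.** The only written formula to which Section 7.3 can point suits the question whether disclosed scores move treatment decisions. In usual care the score is not disclosed, so leaving it out of that arm has a rationale for the decision endpoint. Recurrence and metastasis are different: a prognostic score predicts them whether or not anyone has seen it. A model that gives the score a slope in one arm and none in the other then mixes prognosis with the effect of testing.

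At stake is the trial's patient-outcome claim. An analyst who follows the reference to Section 7.1 literally and reads the arm term as the effect of GC use could report that testing protects against recurrence when the arms do not differ.

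**Working it through.** **Plan's own figure.** There is none to reproduce: the documents give no power, event rate or hazard ratio for Objectives 3 and 4.

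**Inputs from the documents.** 550 subjects and at least 14 centers (Section 3); the three fixed terms (Section 7.1); two-sided 0.05, hence 2.5% in the protective direction (Section 7.3).

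**Inputs assumed.** Score hazard ratio (HR) per 0.1 of 1.1, 1.2 or 1.3; mean score 0.40; three-year BCR from 10% to 40%; positive correlation of score with CAPRA-S.

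**Step 1: algebra under no arm effect.** Let the true log hazard be b·GC + c·CAPRA-S in both arms. The carried-over model fits β1 + β2·GC + β3·CAPRA-S in the GC arm and β3·CAPRA-S in usual care.
- GC-arm men supply the slope, so β2 ≈ b. This is prognosis, not an effect of testing.
- In usual care the average contribution b × mean(GC) has no term and goes into the baseline.
- A GC-arm man at score 0 therefore sits about b × mean(GC) below that baseline, so β1 ≈ −b × mean(GC).

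With h the HR per 0.1, b = 10·ln(h), and the spurious arm HR is about h^(−10 × mean GC) = h^(−4). This is approximate because the shared CAPRA-S coefficient takes up part of the score effect.
- 1.1^(−4) = 1/1.4641 = 0.68
- 1.2^(−4) = 1/2.0736 = 0.48
- 1.3^(−4) = 1/2.8561 = 0.35

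**Step 2: simulation with no arm effect, N = 550, carried-over terms.** Simulation A: score SD 0.22, correlation with CAPRA-S about 0.45, BCR 12% or 20%, 600 trials per setting. Simulation B: Beta(2,3) scores, 14 centers, BCR 10%, 25% or 40%, Cox models stratified by center in place of the frailty term, 400 trials per setting. False protection means significant at two-sided 0.05 in the protective direction.

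| Score HR per 0.1 | h^(−4) | A: arm HR (20% BCR) | A: false protection, 12% / 20% BCR | B: arm HR | B: false protection |
|---|---|---|---|---|---|
| 1.1 | 0.68 | 0.69 | 11% / 15% | 0.62–0.71 | 13–30% |
| 1.2 | 0.48 | 0.47 | 31% / 51% | 0.45–0.49 | 25–78% |
| 1.3 | 0.35 | 0.32 | 58% / 81% | 0.33–0.35 | 47–97% |

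A further run at HR 1.2 and 20% BCR gave an arm HR of 0.48 and false protection in about 47%. With a non-prognostic score (HR 1.0), B gave arm HRs of 0.98–1.03 and two-sided error of 4–7%, so the bias comes from prognosis.

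**Step 3: the other coefficient.** Testing G*GC instead, as the primary analysis does, is no remedy. In B it was significant in 20–46%, 40–90% and 69–99.5% of null trials at the three HRs.

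**Step 4: alternative models, same null data (B, N = 550).**
- G + CAPRA-S: arm HR 0.98–1.02, two-sided error about 4–7%. Counted in the protective direction only, as in the table, 1.8–3.5% at HRs 1.1 to 1.3.
- G + CAPRA-S with a GC main effect in both arms, with or without a centered G*GC term: arm HR 0.96–1.04, two-sided error about 3–7%.

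The Monte Carlo standard error at 5% is √(0.05 × 0.95/400) = 1.1 points.

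**Step 5: Objective 3.** Opposite effects in the two CAPRA-S groups require an arm-by-CAPRA-S term. Neither the carried-over terms nor G + CAPRA-S contains one.

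**The case against.** The strongest reply is that Section 7.3 never says the product term is carried over. Its parenthesis mentions main and random effects, which can fairly be read as arm and CAPRA-S plus center and period. Section 7.5 speaks of fixed effects when it means all the non-random terms, and the SAP writes out or names product terms where it adds them. On that reading the Objective 4 arm test is sound. This stands, and it is why the point is conditional. It does not close the matter: setting main against random also reads naturally as fixed against random, and the GC score clearly belongs to this analysis, since curves by GC risk group are planned.

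Second, no passage says the arm coefficient will be the one reported. True; but the other coefficient carried over does not answer Objective 4 either (Step 3).

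Third, the arm-specific Kaplan-Meier curves would look alike and expose a spurious result. They might, but they are descriptive, and the SAP does not say which result prevails.

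Fourth, the sizes rest on assumptions. That is correct: the documents give no score HR, BCR rate or score distribution for this population. Section 1 supports prognosis for metastasis, while the simulations are for BCR; for BCR the documents offer only a reference title on men treated with postoperative radiation.

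**Conclusion.** The concern holds in conditional form. The survival models and their tested contrasts are not specified, and one plausible reading of the reference to Section 7.1 gives a wrong answer to Objective 4. On that reading, with no true arm effect and assumed score HRs of 1.1 to 1.3 per 0.1, the arm HR is about 0.7 to 0.3. False protection then occurs in roughly 11–81% of trials at 12–20% BCR, against 2.5%. The direction follows whenever the score is adversely prognostic; the size depends on the assumed HR, event rate and mean score.

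A reader might infer more than the documents support:
- **That the SAP certainly reuses the primary formula and tests the arm term.** It states neither.
- **That the fault is the reference point at score 0.** The cause is the absence of a score term in usual care. With a score main effect in both arms, the uncentered arm coefficient is unbiased under no effect, though imprecise and still not the overall effect.
- **That the primary analysis is undermined.** Nothing here bears on it; only secondary objectives are affected.

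Objective 3 is left without a test of its stated hypothesis on either reading.

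**What to change.** Write the models out in Section 7.3 and name one tested contrast per objective, before outcome data are analyzed.

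- **Objective 4 (BCR and metastasis).** Fit G and CAPRA-S with the center and period terms and no G*GC, and test the coefficient of G. Alternatively, if GC scores are generated for usual-care men from the tissue collected in both arms, add the score as a main effect in both arms and report the arm HR from that model; center the score if a product term is also kept.
- **Objective 3 (salvage).** Add a G-by-CAPRA-S term using the SAP's own grouping (below 5, 5 or more), test that term, and report the arm HR within each group. A single arm HR would average effects predicted to run in opposite directions.
- **Score-specific contrasts.** Keep these separate and label them descriptive.

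The cost is SAP wording, with no extra patients or data collection. The alternative for Objective 4 additionally depends on scores being produced for the usual-care arm.
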